Protocol Number: 0761-014 
and other baseline characteristic information will be summarized for the Safety Analysis and Efficacy Analysis Sets. Adverse events will be tabulated by body system, severity, and relation to treatment. Similar presentations will be provided for SAEs, AEs leading to discontinuation of IMP and AEs leading to death. The tabulation of laboratory parameters will indicate the normal range for each parameter. Each value will be classified as falling above, below, or within the normal range.
 
Individual serum concentrations at each sampling time point for mogamulizumab and nivolumab will be presented in listings. Descriptive summary statistics of serum concentrations including means, geometric means, ranges, standard deviations, and coefficient of variation will be presented by dose cohort and by tumor type. Dose proportionality will be assessed as appropriate. Population PK analysis will be explored, if appropriate.
 
Pharmacodynamic data will be summarized. Changes from baseline in PD parameters may be used as PD markers to explore PK/PD, PD-efficacy, and PD-safety relationships, as appropriate.
 
The number and percentage of subjects with a positive anti-drug antibody (ADA) test in the screening, confirmatory, or neutralizing assays, if applicable, will be presented at each visit and overall for subjects exposed to mogamulizumab and nivolumab. Additionally, a summary of subjects who experienced an infusion related reaction and had a positive ADA test in the screening, confirmatory, and neutralizing assays, if applicable, will be presented. All immunogenicity data will be listed by subject. Immunogenicity may be reported for ADA positive status (such as persistent positive, neutralizing positive, only last sample positive, baseline positive and other positive) and ADA negative status, relative to baseline. Effect of immunogenicity on safety, efficacy, biomarkers and PK may be explored.
 
Subjects will be evaluated for tumor response, TTR, DOR, and PFS. The ORR will be calculated as the proportion of subjects who are responders, i.e., complete response (CR) and partial response (PR); the 95% exact confidence interval for ORR will be calculated. The ORR will be derived using both the RECIST v. 1.1 and the irRECIST v. 1.1, based on the efficacy-evaluable subjects in the expansion cohorts for combination therapy, which includes all subjects who receive combination therapy in Cycle 1 Day 1. Duration of response, OS, and PFS will be estimated using the Kaplan-Meier methodology.

### **3 LIST OF ABBREVIATIONS AND DEFINITION OF TERMS**

#### **Abbreviations**

ACTH	adrenocorticotrophic hormone
ADA	anti-drug antibody
ADCC	antibody-dependent cellular cytotoxicity
ADP	adenosine diphosphate
AE	adverse event
ALK	anaplastic lymphoma kinase
ALT	alanine transaminase
AST	aspartate transaminase
ATL	adult T-cell leukemia/lymphoma
BMS	Bristol-Myers Squibb
BOR	best overall response
CCR4	chemokine receptor 4
CD	cluster of differentiation
CDC	complement dependent cytotoxic
CFR	Code of Federal Regulations
CI	confidence interval
CL	clearance
CNS	central nervous system
CR	complete response
CRC	colorectal carcinoma
CrCL	creatinine clearance
CSR	clinical study report
CTCAE	Common Terminology Criteria for Adverse Events
CTCL	cutaneous T-cell lymphoma
CTLA-4	cytotoxic T-lymphocyte-associated antigen-4
CT	computed tomography
DLT	dose-limiting toxicity
DOE	duration of response
ECG	electrocardiogram
ECOG	Eastern Cooperative Oncology Group
eCRF	electronic Case Report Form
EDC	Electronic Data Capture
EGFR	epidermal growth factor receptor
EOT	end of treatment
EU	European Union
Fc	fragment crystallizable
FDA	Food and Drug Administration
FDG	fluorodeoxyglucose
FFPE	formalin-fixed, paraffin-embedded
GCP	Good Clinical Practices
HBVsAg	Hepatitis B surface antigen
HCC	hepatocellular carcinoma
HIPAA	Health Insurance Portability and Accountability Act

## Abbreviations

HIV	human immunodeficiency virus
HPV	human papillomavirus
HR	hazard ratio
IB	Investigator's Brochure
ICF	informed consent form
ICH	International Conference on Harmonization
ICOS	inducible T-cell costimulator
ID	identification
IFN- $\gamma$	interferon- $\gamma$
IgG	immunoglobulin G
IHC	immunohistochemistry
IL	interleukin
IMP	investigational medicinal product
irCR	irRECIST-defined complete response
IRB	Institutional Review Board
irPD	irRECIST-defined progressive disease
irRECIST	immune-related Response Evaluation Criteria in Solid Tumors
IRT	interactive response technology
iv	Intravenous
KKD	Kyowa Kirin Pharmaceutical Development
LFT	Liver function test
mAb	monoclonal antibody
MDC	macrophage-derived chemokine
MRI	magnetic resonance imaging
MSI	microsatellite instability
MSI-H	microsatellite instability - high
MSI-L	microsatellite instability - low
MSS	microsatellite - stable
MTD	maximum tolerated dose
NOEAL	no-observed-adverse-effect level
NSCLC	non-small-cell lung cancer
ORR	overall response rate
OS	overall survival
PARP	poly ADP ribose polymerase
PD	pharmacodynamic(s)
PD-1	programmed death 1
PD-L1	programmed cell death ligand 1
PD-L2	programmed cell death ligand 2
PCR	polymerase chain reaction
PET	positron emission tomography
PFS	progression-free survival
PI	Prescribing Information
PK	pharmacokinetic(s)
PR	partial response
PS	performance status

## Abbreviations

PTCL	peripheral T-cell lymphoma
RECIST	Response Evaluation Criteria in Solid Tumors
RNA	ribonucleic acid
SAE	serious adverse event
SCCHN	Squamous cell carcinoma of the head and neck
SCID	severe combined immunodeficiency
SRC	Safety Review Committee
TARC	thymus and activation-regulated chemokine
TEAE	treatment-emergent adverse event
Th2	T-helper 2 subset of T-cells
TNF- $\alpha$	tumor necrosis factor-alpha
TMTB	total measured tumor burden
T reg	regulatory T-cells
TTR	time to response
ULN	upper limit of normal
US	United States (of America)

## Definitions

AUC 0-7 days	area under the concentration-time curve from Day 0 to Day 7
C max	observed peak serum concentration
C min	observed minimum serum concentration at the end of a dosing interval
pH	hydrogen ion concentration
t 1/2	terminal half-life

## 4 INTRODUCTION

## 4.1 Medical Background

#### 4.1.1 Immunotherapy for Cancer

Topic	Percentage
Donald Trump	98
North Korea	97
U.S. presidential election, 2016	96
U.S. Congress	95
U.S. Supreme Court	94
U.S. state of California	93
U.S. state of Texas	92
U.S. state of New York	91
U.S. state of Florida	90
U.S. state of Illinois	89
U.S. state of Michigan	88
U.S. state of Pennsylvania	87
U.S. state of Ohio	86
U.S. state of Wisconsin	85
U.S. state of Minnesota	84
U.S. state of Washington	83
U.S. state of Oregon	82
U.S. state of Virginia	81
U.S. state of North Carolina	80
U.S. state of South Carolina	79
U.S. state of Georgia	78
U.S. state of Mississippi	77
U.S. state of Louisiana	76
U.S. state of Alaska	75
U.S. state of Hawaii	74
U.S. state of Rhode Island	73
U.S. state of Connecticut	72
U.S. state of Massachusetts	71
U.S. state of Vermont	70
U.S. state of New Hampshire	69
U.S. state of Maine	68
U.S. state of Alaska	67
U.S. state of Hawaii	66
U.S. state of Rhode Island	65
U.S. state of Connecticut	64
U.S. state of Massachusetts	63
U.S. state of Vermont	62
U.S. state of New Hampshire	61
U.S. state of Maine	60
U.S. state of Alaska	59
U.S. state of Hawaii	58
U.S. state of Rhode Island	57
U.S. state of Connecticut	56
U.S. state of Massachusetts	55
U.S. state of Vermont	54
U.S. state of New Hampshire	53
U.S. state of Maine	52
U.S. state of Alaska	51
U.S. state of Hawaii	50
U.S. state of Rhode Island	49
U.S. state of Connecticut	48
U.S. state of Massachusetts	47
U.S. state of Vermont	46
U.S. state of New Hampshire	45
U.S. state of Maine	44
U.S. state of Alaska	43
U.S. state of Hawaii	42
U.S. state of Rhode Island	41
The Black Lives Matter movement	41
The Epstein-Ghislaine scandal	11

## 4.2 Investigational Medicinal Products Profile

[figure not shown]
#### 4.2.1 Mogamulizumab

Term	Percentage
GDP	98%
Inflation	98%
Interest rates	98%
Central bank	98%
Monetary policy	98%
Quantitative easing	98%
Inflation targeting	98%
Interest rate hike	98%
Interest rate cut	98%

[figure not shown]
Redacted content consisting of approximately 15 lines of text.

#### **4.2.1.1 Nonclinical Experience**

Redacted content consisting of approximately 20 lines of text.

#### **4.2.1.2 Clinical Pharmacology**

Redacted content consisting of approximately 10 lines of text.

11. **What is the primary purpose of the *Journal of Clinical Endocrinology and Metabolism*?**

#### 4.2.1.3 Clinical Experience

#### 4.2.1.4 Post-marketing Experience

113  
114  
115

## 4.2.2 Nivolumab

Term	Percentage (%)
GDP	95
Inflation	95
Interest rates	95
Central bank	95
Monetary policy	95
Quantitative easing	95
Inflation targeting	95
Interest rate hike	95
Interest rate cut	95
Interest rate parity	95
Nominal interest rate	95
Real interest rate	95
Nominal GDP	95
Real GDP	95
Nominal exchange rate	85
Real exchange rate	85
Nominal income	85
Real income	85

#### 4.2.2.1 Nonclinical Experience

A horizontal bar chart consisting of five solid black bars of increasing length from left to right. The bars are separated by small gaps. The first bar is the shortest, and the fifth bar is the longest, extending almost to the right edge of the frame.

#### 4.2.2.2 Clinical Pharmacology

#### 4.2.2.3 Clinical Experience

Term	Percentage
GDP	85
Inflation	90
Interest rates	100
Central bank	88
Monetary policy	85
Quantitative easing	82
Inflation targeting	80
Interest rate hike	85

#### 4.2.3 Clinical Experience with the Combination of Mogamulizumab and Nivolumab

Term	Percentage
GDP	85%
Inflation	82%
Interest rates	80%
Central bank	78%
Monetary policy	75%
Quantitative easing	72%
Inflation targeting	68%
Interest rate hike	65%

### 4.3 Selection of Doses in the Study

#### 4.3.1 Mogamulizumab

### 4.3.2 Nivolumab

A horizontal bar chart comparing the percentage of the population aged 65 and older in 2010 across 20 countries. The x-axis represents the percentage of the population aged 65 and older in 2010, ranging from 10% to 30%. The y-axis lists the countries. The bars are black and show the following approximate values:

[figure not shown]
Country	Percentage (2010)
Argentina	10.1%
Australia	11.8%
Austria	12.1%
Belgium	12.2%
Brazil	12.3%
Canada	12.5%
Chile	12.6%
Costa Rica	12.7%
Czech Republic	12.8%
Denmark	12.9%
Finland	13.0%
France	13.1%
Germany	13.2%
Greece	13.3%
Hungary	13.4%
Italy	13.5%
Japan	13.6%
Mexico	13.7%
Netherlands	13.8%
Norway	13.9%
Portugal	14.0%
Spain	14.1%
Sweden	14.2%
Switzerland	14.3%
Turkey	14.4%
United Kingdom	14.5%
United States	14.6%

Term	Percentage
GDP	100%
Inflation	100%
Interest rates	100%
Central bank	100%
Monetary policy	100%
Quantitative easing	100%
Institutional investors	100%
Fintech	100%
Algorithmic trading	100%
Blockchain	100%

#### 4.4 Rationale for Combination Treatment

**Figure 4.4-1 Depletion of CD4+ CD25+ FOXP3+ Cells**

[figure not shown]
Numbers of CD4+ CD25+ FOXP3+ cells from mogamulizumab–treated subjects with adult T-cell leukemia-lymphoma (ATL) in blood samples taken (i) just before the first infusion, (ii) just before the second infusion, (iii) just before the fifth infusion, (iv) 1 week after the eighth infusion, and (v) 4 months after the eighth infusion and those from 10 controls are shown as box and whisker plots indicating minimum, lower quartile, median, upper quartile, and maximum values.

#### 4.5 Tumor Types for Expansion Cohorts in Phase 2

[figure not shown]

**4.5.1 NSCLC Squamous Cell**

The content of this section has been completely redacted with black bars of varying lengths.

**4.5.2 NSCLC Nonsquamous Cell**

The content of this section has been completely redacted with black bars of varying lengths.

#### **4.5.3 Squamous Cell Carcinoma of the Head and Neck**

#### **4.5.4 Colorectal Cancer**

**4.5.5 Ovarian Cancer**

[REDACTED]

**4.5.6 Hepatocellular Carcinoma**

[REDACTED]

**4.5.7 Pancreatic Adenocarcinoma**

[REDACTED]

**4.6 Risks and Benefit to Subjects**

[REDACTED]

## **5 OBJECTIVES**

### **5.1 Primary**

To characterize the safety and tolerability and determine the maximum tolerated dose (MTD), or the highest protocol-defined dose in the absence of exceeding the MTD, of the combination regimen of mogamulizumab and nivolumab in subjects with locally advanced or metastatic solid tumors.

### **5.2 Secondary**

- 1) To evaluate the anti-tumor activity of the combination of mogamulizumab and nivolumab based on the RECIST v. 1.1. Anti-tumor activity will be assessed as ORR, time to response (TTR), duration of response (DOR), PFS, and OS.

### **5.3 Exploratory**

- 1) To assess serum concentrations of mogamulizumab and nivolumab when administered in combination.
- 2) To evaluate the immunogenicity of mogamulizumab and nivolumab when administered in combination.
- 3) To evaluate the PD profile of the combination of mogamulizumab and nivolumab and determine which biomarkers may correlate with safety and/or anti-tumor activity.
- 4) To evaluate the ORR of the combination of mogamulizumab and nivolumab based on the irRECIST v. 1.1.

## **6 DESCRIPTION OF STUDY DESIGN AND POPULATION**

### **6.1 Study Overview**

This is a multicenter, Phase 1/2, open-label, dose-finding and cohort-expansion study of the anti-CCR4 antibody mogamulizumab in combination therapy with the anti-PD-1 antibody nivolumab in adult subjects with locally advanced or metastatic solid tumors. Subjects will be screened for entry into this study after signing the informed consent form (ICF). Subjects who meet study entry criteria will enter the treatment cohort that is open to enrollment.

The study includes a Phase 1 dose finding and a Phase 2 cohort-expansion:

- Phase 1 dose-finding has a 3+3 design that will identify the MTD, or the highest protocol-defined dose in the absence of exceeding the MTD, for the combination regimen and will enroll up to 12 subjects (3 to 6 subjects per cohort).
- Phase 2 cohort-expansion will explore the safety, PK, PD, and anti-tumor activity of the highest tolerated dose of the combination regimen and will enroll up to 184 subjects (21 to 36 per cohort) in up to 7 tumor-specific expansion cohorts.

### 6.1.1 Phase 1: Dose Finding

A starting dose level and an optional dose level are planned. The dose-finding phase will enroll up to 12 subjects (3 to 6 subjects per cohort). The dose levels and schedules are described in [Table 6.1.1-1](#).

The MTD is defined as one dose level below the dose level of the cohort where  $\geq$  one-third of the subjects experience DLT. The recommended dose regimen for Phase 2 is intended to be either the MTD or the highest dose level tested.

**Table 6.1.1-1 Dose Levels**

Dose Level	Dosage of Mogamulizumab		Dosage of Nivolumab
	Cycle 1 (Days 1, 8, 15, 22)	Subsequent Cycles (Days 1, 15)	All Cycles (Days 1, 15)

a: This dose level may be enrolled if  $> 1$  subject experiences DLT at Dose Level 1.

DLT=dose limiting toxicity.

A minimum of 3 subjects will be enrolled and treated in each cohort, and all 3 subjects will be observed for the DLT observation period (see Section [6.1.2.1](#)). Subjects who are not evaluable for DLT will be replaced. All cohorts will have a minimum of 3 DLT-evaluable subjects. Cycle 1 Day 1 dosing of subjects in each cohort should be separated by at least 1 day during Phase 1 of the study.

### 6.1.2 Dose-finding Criteria

[figure not shown]
A Safety Review Committee (SRC) composed of physicians from the Sponsor and/or designee and Investigators will review cumulative safety data from all subjects before deciding whether to change the dose level or open the expansion cohorts.

The first meeting of the SRC will occur before the study opens to enrollment. At that meeting the SRC will discuss the role and responsibilities of the SRC and review the safety data from the ongoing 0761-013 Phase 1 study. In that study, nivolumab is administered at 3.0 mg/kg and mogamulizumab has been administered at 0.3 mg/kg or 1.0 mg/kg. The SRC may decide to open Phase 1 of this study at the optional dose level if there is concern about the safety of the combination at the higher dose level in the Japanese trial.

Dose finding will continue until an MTD has been established or it is determined that the expansion cohorts should open or that dosing should stop. Further exploration of intermediate doses may take place based on evaluation of emerging safety and PK/PD parameters in the

current trial as well as other ongoing trials. The criteria for dose finding are outlined in [Figure 6.1-1](#).

**Figure 6.1-1 Criteria for Dose Finding and Expansion**

See [Table 6.1.1-1](#) for dose levels. DLT=dose-limiting toxicity.

### 6.1.2.1 Definition of Dose-limiting Toxicity

A DLT is defined as the occurrence of any of the following toxicities that are considered **related to IMP**, with onset from the first dose to 14 days after the last dose of IMP in Cycle 1:

#### *Hematologic Toxicity*

- 1) Grade 3 thrombocytopenia with clinically significant bleeding;
- 2) Grade 4 thrombocytopenia;
- 3) Febrile neutropenia (absolute neutrophil count  $< 500/\text{mm}^3$  with a single temperature of  $> 38.3^\circ\text{C}$  [ $101^\circ\text{F}$ ]);

- 4) Grade 4 neutropenia of duration > 7 days;

Note: Grade  $\geq$  3 lymphopenia or leukopenia of any duration is not considered a DLT.

*Non-hematologic Toxicity*

- 5) Aspartate transaminase (AST) or alanine transaminase (ALT) elevation  $> 5$  to  $\leq 10$  times the upper limit of normal (ULN) (Grade 3) that does not downgrade to  $\leq$  Grade 1 (or to baseline grade if  $>$  Grade 1 at baseline) within 14 days;
- 6) AST or ALT elevation  $> 10$  times ULN;
- 7) Total bilirubin  $> 5$  times ULN;
- 8) ALT or AST elevation  $> 3$  times ULN AND concomitant total bilirubin  $> 2$  times ULN, without initial findings of cholestasis (elevated serum alkaline phosphatase), AND no other immediately apparent possible causes of ALT/AST elevation and hyperbilirubinemia, including, but not limited to, tumor progression, viral hepatitis, pre-existing chronic or acute liver disease, or the administration of other drug(s) known to be hepatotoxic;
- 9) A  $\geq$  Grade 3 non-hematologic laboratory AE (other than AST, ALT, or bilirubin) is a DLT only if it requires medical intervention or hospitalization. Exception: Grade 3 or Grade 4 electrolyte abnormalities that are not associated with clinical signs or symptoms, and either resolve spontaneously or respond to conventional medical intervention are not DLTs;

Note:  $\geq$  Grade 3 elevation of amylase and/or lipase of any duration not associated with clinical or radiographic evidence of pancreatitis is not a DLT;

- 10) Grade 4 non-hematologic non-laboratory AE;
- 11) Grade 3 skin rash that does not improve to  $\leq$  Grade 2 within 3 days of initiation of maximal supportive care;
- 12) Grade 3 uveitis, bronchospasm, or neurologic toxicity of any duration;
- 13) Any other Grade 3 non-hematologic non-laboratory AE lasting  $> 7$  days, with the following exceptions:
  - a) Grade 3 inflammatory reaction attributed to a local antitumor response (e.g., inflammatory reaction at sites of metastatic disease, lymph nodes, tumor lysis syndrome) is not a DLT;
  - b) Grade 3 fatigue is not a DLT;
  - c) Grade 3 fever not associated with hemodynamic compromise is not a DLT;
- 14) Grade 2 or higher pneumonitis of any duration;
- 15) Any Grade 2 uveitis, eye pain, or blurred vision that does not respond to topical therapy and does not improve to Grade 1 within 14 days OR requires systemic treatment.

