### **6.1.3 Phase 2: Expansion Cohort**

To further characterize the safety, tolerability, and anti-tumor activity of the combination, up to 184 subjects (21 to 36 subjects per tumor type) with locally advanced or metastatic disease in the following tumor types will be enrolled: squamous cell NSCLC; PD-L1-non-expressing non-squamous cell NSCLC; SCCHN; colorectal carcinoma, non-microsatellite instability (non-MSI) high; hepatocellular carcinoma (HCC), pancreatic adenocarcinoma, and ovarian cancer (including primary peritoneal cancer and fallopian tube carcinoma). Subjects will be treated with the highest dose of the combination regimen that was considered tolerable in Phase 1.

The SRC will review cumulative safety data from all subjects approximately every 2 months during the enrollment period. Clinical safety in the expansion cohorts will be monitored continually. If the rate of AEs meeting DLT definitions during the expansion portion of the study is  $> 1/3$  in at least 3 evaluable subjects within a cohort, these findings will be discussed by the SRC, in the context of all available safety information, to determine whether enrollment to that cohort and/or the remaining cohorts should be suspended, whether a lower dose should be examined, or whether any additional monitoring or treatment requirements should be implemented.

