### **7.5.1 Replacement of Subjects**

Subjects in Phase 1 will be considered nonevaluable for DLT and will be replaced if they do not experience a DLT and:

- they do not receive all infusions of both IMPs in Cycle 1 within 28 days at the doses assigned to the cohort in which they are enrolled, or
- they do not complete the safety follow-up through the end of the DLT evaluation period (Section [6.1.2.1](#)).

Subjects enrolled in Phase 2 may be replaced, for these same reasons, at the discretion of the Sponsor.

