4.13.1 Adverse Events

All subjects will be assessed regularly for the potential occurrence of adverse events (AEs) from the date of informed consent to 100 days after the last dose of IMP. The incidence of treatment-emergent AEs (TEAEs) will be summarized and tabulated using MedDRA (version 18.1), by System Organ Class (SOC) and Preferred Term (PT). A TEAE is defined as an AE that first occurs or worsens in severity on or after the first dose of any IMP and within 100 days after the last dose of IMP.

The National Cancer Institute Common Terminology Criteria for Adverse Events (CTCAE) (Version 4.03) will be used to grade both clinical and laboratory AEs. A subject with several occurrences of the same AE will be counted once and classified by the most severe occurrence. AEs with missing severity ratings will be classified as having unknown severity, but will be assigned Grade 3 severity for analysis and summarization.

The relationship of each AE to the IMP will be classified as related or unrelated. Any AE with an eCRF description of related will be considered related. A subject with several occurrences of the same AE will be counted once and classified as related if at least one of them is classified as related. An AE with a missing relationship to IMP will be assumed to be related to IMP for the purpose of analysis and summarization. Relationship of AEs to mogamulizumab and nivolumab will be separately recorded and analyzed.

An overview of adverse events for the Safety Analysis Set will be provided, summarizing the incidence of the following:

- Any TEAEs; Mogamulizumab-related TEAEs; Nivolumab-related TEAEs;
- Any NCI/CTCAE Grade 3/4/5 TEAEs; Mogamulizumab-related NCI/CTCAE Grade 3/4/5 TEAEs; Nivolumab-related NCI/CTCAE Grade 3/4/5 TEAEs;
- Any Treatment-emergent SAEs; Mogamulizumab-related treatment-emergent SAEs; Nivolumab-related treatment-emergent SAEs;
- Any discontinuation of study drug due to TEAEs; discontinuation of Mogamulizumab due to Mogamulizumab-related TEAEs; discontinuation of Nivolumab due to Nivolumab-related TEAEs;
- Any NCI/CTCAE Grade 5 TEAEs; Mogamulizumab-related NCI/CTCAE Grade 5 TEAEs; Nivolumab-related NCI/CTCAE Grade 5 TEAEs;

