Table 14.3.1.13.2	Number (%) of Subjects with Nivolumab-Related Treatment-Emergent Fatal Adverse Events By System Organ Class and Preferred Term - Safety Analysis Set
Table 14.3.1.13.3	Number (%) of Subjects with Any IMP-Related Treatment-Emergent Fatal Adverse Events By System Organ Class and Preferred Term - Safety Analysis Set
Table 14.3.1.14	Number (%) of Subjects with Treatment-Emergent Infusion Reaction Adverse Events By Preferred Term - Safety Analysis Set
Table 14.3.2.1	Summary of Clinical Laboratory Values and Change from Baseline During Treatment Period - Safety Analysis Set
Table 14.3.2.2.1	Shift Table for Laboratory Parameters with Single Direction - Safety Analysis Set
Table 14.3.2.2.2	Shift Table for Laboratory Parameters with Both Low and High Directions - Safety Analysis Set
Table 14.3.3.1	Summary of Vital Signs and Change from Baseline During Treatment Period - Safety Analysis Set
Table 14.3.4.1	Summary of ECG Evaluations and Change from Baseline During Treatment Period - Safety Analysis Set
Table 14.3.4.2	Number (%) of Subjects with Abnormal QTcB and QTcF (msec)

Tables

	During Treatment Period - Safety Analysis Set
Table 14.3.4.3	Shift Table for QTcB and QTcF (msec) from Baseline During Treatment Period - Safety Analysis Set
Table 14.3.5.1	Summary of Weight and Change from Baseline During Treatment Period - Safety Analysis Set
Table 14.3.6.1	Worst ECOG Performance Status Result During Treatment Period - Safety Analysis Set
Table 14.4.1.1	Summary of PK Parameters (Cmax and Cmin) of Mogamulizumab - Pharmacokinetic Analysis Set
Table 14.5.1.1	Number (%) of Subjects with Positive Anti-Drug Antibody Response to Mogamulizumab - ADA Analysis Set
Table 14.5.2.1	Summary of Anti-Mogamulizumab Antibody Incidence - ADA Analysis Set
Table 14.5.3.1	Summary of Positive Anti-Mogamulizumab Antibody Response at Post-Baseline and Infusion Reaction - Safety Analysis Set

Figures

Figure 14.2.1	Kaplan-Meier Curve of Progression-Free Survival - Efficacy Analysis Set
Figure 14.2.2	Kaplan-Meier Curve of Overall Survival - Efficacy Analysis Set
Figure 14.2.3.1	Percent Change in Tumor Burden (RECIST v1.1)– Efficacy Analysis Set
Figure 14.2.3.2	Percent Change in Tumor Burden (irRECIST v1.1) – Efficacy Analysis Set
Figure 14.2.4.1.1	Maximum Percent Change in Tumor Burden by Best Overall Response (RECIST v1.1)– Efficacy Analysis Set

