Subject (Age/Gender)	Cancer Type	VT: Verbatim Term PT: MedDRA Preferred Term SOC: System Organ Class	Start Date	Stop Date	Start	Time	CTCAE Grade	Serious	Relationship Mogamulizumab/ Nivolumab	Action Taken Mogamulizumab/ Nivolumab/Treated?	Outcome/ DLT?
			Time/Day [1]	Time/Day	Cycle/ Cycle						
xxx-xxx (xx/F)	Lung	VT: xxxxxxxxxxxxxxxxxxxx*	YYYY-MM- DD/xx	xx/xx	DMI	x	No	NR/ NR	NN/ NR/No	REC/ No	
		PT: xxxxxx SOC: xxxxxx	YYYY-MM- DD/xx								
		VT: xxxxxxxxxxxxxxxxxxxx	YYYY-MM- DD/xx	xx/xx	PTM	x	No	R/ NR	DR/ NN/Yes	NREC/ Yes	
		PT: xxxxxx SOC: xxxxxx	YYYY-MM- DD/xx								

Continue with Expansion phase (Mogamulizumab x mg/kg + Nivolumab 240 mg).

[1] Day = Start/Stop date of adverse event - First dose date of the study drug (+1 if Start/Stop Date ≥ First dose date of the study drug); Cycle Day = Start date of adverse event - closest prior cycle Day 1 + 1.
 [2] Duration = Stop date of adverse event - Start date of adverse event + 1.
 Time point: NOI = N/A; PNI = Pre-Nivolumab Infusion; DNI = During Nivolumab Infusion; PTN = Post Nivolumab Infusion; PMI = Pre-Mogamulizumab Infusion; DMI = During Mogamulizumab Infusion; PTM = Post Mogamulizumab Infusion; UNK = Unknown.
 CTCAE Grade: 1 = Grade 1 (Mild); 2 = Grade 2 (Moderate); 3 = Grade 3 (Severe or Disabling); 4 = Grade 4 (Life-threatening); 5 = Grade 5 (Death).
 Relationship: NR = Not Related; R = Related.
 Action Taken: NN = None; DW = Drug Withdrawn; DR = Decrease Infusion Rate; DI = Dose Interrupted/Delayed; PA = Prior to Administration of SD/IP.
 Outcome: REC = Recovered/Resolved; NREC = Not Recovered/Not Resolved; RECS = Recovered/Resolved with Sequelae; RRC = Recovering/Resolving; FAT = Fatal; UNK = Unknown.
 * Non-treatment emergent event;
 Note: MedDRA Version 18.1 was used for coding.

The following listings will have similar layout as Listing 16.2.7.1:

Listing 16.2.7.2
Mogamulizumab or Nivolumab-related Adverse Events

Listing 16.2.7.3
Grade ≥ 3 Adverse Events

Listing 16.2.7.4
Serious Adverse Events (SAEs)

Listing 16.2.7.5
Adverse Events Leading to Discontinuation of Mogamulizumab or Nivolumab

Listing 16.2.7.6
Fatal Adverse Events

Listing 16.2.7.7
Infusion Reaction Adverse Events

Listing 16.2.8.1
 Laboratory Assessment - Chemistry

Treatment = Phase 1: Dose finding phase (Mogamulizumab 1 mg/kg + Nivolumab 240 mg)

Subject	Cancer Type	Lab Test (Unit)	Normal Range Low-High	Cycle	Sample Date (Days [1])	Lab Value	Flag	CTCAE Grade

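### DLT item 10 stops at Grade 4, so read literally a drug-related death that was not pneumonitis, was not first recorded at Grade 4 and met no other item is not a DLT (minor)

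*Protocol*

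**What the plan says.** Protocol 6.1.2.1 lists 15 kinds of related event, with onset from first dose to 14 days after the last Cycle 1 dose, that count as dose-limiting. Item 10 is "Grade 4 non-hematologic non-laboratory AE", and the synopsis has the same words. Item 14, by contrast, is open-ended: "Grade 2 or higher pneumonitis of any duration". Severity follows CTCAE v4.03 (Protocol 10.3.1.4), and the key to SAP Listing 16.2.7.1 separates the top two grades: "4 = Grade 4 (Life-threatening); 5 = Grade 5 (Death". Neither document states that a Grade 5 event is a DLT, and the SAP does not redefine the term.

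DLT status is used in three places:

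- **MTD (6.1.2.2).** It is set by a DLT proportion of at least one third in a cohort.
- **Replacement (7.5.1).** "Subjects in Phase 1 will be considered nonevaluable for DLT and will be replaced if they do not experience a DLT and" either missed part of Cycle 1 dosing or did not finish follow-up through the DLT window. In Phase 2, replacement for these reasons is at the sponsor's discretion.
- **Expansion trigger (6.1.3).** "If the rate of AEs meeting DLT definitions during the expansion portion of the study is" above one third, with at least three evaluable subjects in a cohort, the Safety Review Committee (SRC) discusses the findings "in the context of all available safety information".

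Separately, the laboratory bullet in the dose-delay criteria (8.1.2.2) names Grade 3 only, while its own amylase/lipase exception is written for Grade 3 and above.

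**The concern.** The authors wrote open ranges where they wanted them (items 9 and 14), and the trial's key gives death its own grade. A person coding strictly from the text therefore has no item under which to place a sudden related death. The most severe toxicity would be marked as not dose-limiting, although a Grade 4 event of the same kind would qualify. At stake are the Phase 1 DLT count, the numerator of the Phase 2 discussion trigger, and the DLT flag that goes into the study report.

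**Working it through.** **Step 1. A related Grade 5 clinical event against each DLT item.**

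| Items | Scope | Reaches Grade 5 clinical event? |
|---|---|---|
| 1–4 | haematologic | not applicable |
| 5–9 | laboratory (item 9 is Grade 3 and above) | not applicable |
| 10 | Grade 4 clinical | no |
| 11–13 | Grade 3 clinical | no |
| 14 | pneumonitis, Grade 2 and above | yes, pneumonitis only |
| 15 | Grade 2 eye events | no |

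A fatal event can still qualify on the way to death: through Grade 4 (item 10), through Grade 3 bronchospasm or neurologic toxicity (item 12), or through liver values (items 5–8). What escapes is a death that met none of these first.

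**Step 2. Phase 1.** One such death in a cohort of 3 should read 1/3. Literally it adds 0, and if Cycle 1 dosing or DLT follow-up was cut short the subject is replaced, so the cohort reads 0/3. If the event began in the window, all Cycle 1 doses were given and follow-up ran to the end of the window, 7.5.1 does not call for replacement. Phase 1 closed with 4 subjects (6.2).

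**Step 3. Phase 2, one death.** The trigger fires when DLTs/n > 1/3, n ≥ 3. Assume the subject stays in the denominator, since 7.5.1 does not say otherwise. Let k be the number of other DLTs. The result changes only if k/n ≤ 1/3 < (k+1)/n, that is k = floor(n/3): exactly one value of k for each n from 3 to 36. At the Stage 1 sizes in Table 12.3.1-1 that are below 15, plus 16:

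| n | As written | Death counted |
|---|---|---|
| 10 | 3/10 = 30.0% | 4/10 = 40.0% |
| 12 | 4/12 = 33.3% | 5/12 = 41.7% |
| 14 | 4/14 = 28.6% | 5/14 = 35.7% |
| 16 | 5/16 = 31.3% | 6/16 = 37.5% |

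These are the pivotal counts only. Given one such death, and each of the other n−1 subjects having another DLT with probability 10%, the chance of being at the pivotal count in a single look is:

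- n=10: C(9,3) × 0.1³ × 0.9⁶ = 84 × 0.001 × 0.5314 = 4.5%
- n=21: C(20,7) × 0.1⁷ × 0.9¹³ = 77520 × 10⁻⁷ × 0.2542 = 0.2%

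**Step 4. Chance that the trigger fires.** Let p be the per-subject rate of other DLTs and q the rate of deaths that escape the list, mutually exclusive. The DLT count is Binomial(n, p) as written and Binomial(n, p+q) if the deaths count. At n=21 the trigger needs at least 8 events. Multiple looks are handled by exact recursion. The documents give no p, q or look schedule, so all are assumptions. Each cell shows as written against counted:

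| p, q | One look, n=21 | Looks at 10 and 21 | Every subject, 3 to 21 |
|---|---|---|---|
| 10%, 0.5% | 0.06% / 0.09% | 1.30% / 1.55% | 9.6% / 10.6% |
| 10%, 2% | 0.06% / 0.20% | 1.30% / 2.47% | 9.6% / 13.7% |
| 20%, 5% | 4.31% / 12.99% | 13.51% / 26.40% | 35.7% / 51.8% |

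The last row needs both a high background DLT rate and 1 subject in 20 dying in a way that no item captures.

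**Step 5. Companion laboratory rule.** A related Grade 4 laboratory event that is a DLT goes to discontinuation (8.1.4). One that is not a DLT, such as Grade 4 neutropenia lasting 7 days or less (item 4 requires more than 7) or a symptom-free Grade 4 electrolyte change that resolves (exception in item 9), meets neither 8.1.4 nor the literal Grade 3 bullet. The same event at Grade 3 requires a delay.

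**The case against.** The strongest reply is that the intent is plainly Grade 4 or worse, that no reasonable investigator or committee would ignore a drug-related death, and that little now turns on the wording. Much of this stands. Related deaths are SAEs reported within 24 hours (10.3.2.2.1). The SRC reviewed the accumulated safety data of every subject, not DLTs alone. The SAP overview includes "Any NCI/CTCAE Grade 5 TEAEs; Mogamulizumab-related NCI/CTCAE Grade 5 TEAEs; Nivolumab-related NCI/CTCAE Grade 5 TEAEs", and Table 14.3.1.13.3 gives "Number (%) of Subjects with Any IMP-Related Treatment-Emergent Fatal Adverse Events". The SAP plans no DLT-rate table; DLT appears in its outputs only as a column of Listing 16.2.7.1. Phase 1 is closed, and the SRC was disbanded as of Amendment 3 (8.1.2.1).

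A reader might go further and infer any of the following. The documents support none of them.

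- *All fatal clinical events other than pneumonitis escape.* Step 1 shows that those first recorded at Grade 4, or meeting another item, are already DLTs.
- *A Phase 1 subject who died would always be replaced.* 7.5.1 requires incomplete Cycle 1 dosing or incomplete DLT-window follow-up.
- *A stopping rule would fail.* The one-third rate prompts a discussion and binds no one to stop.
- *Deaths would be hidden.* The reporting and tables above show them.

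On the laboratory rule, the reply is that the exceptions make sense only if the bullet reaches above Grade 3, that a Grade 4 value recovering through Grade 3 then meets the literal rule, and that the investigator may delay for any abnormality. That makes the gap minor. It does not close it, because the judgement clause leaves delay at Grade 4 to the investigator while Grade 3 requires it.

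Clear intent does not fill the gap in item 10 either: someone must still enter yes or no in the DLT column.

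**Conclusion.** The point holds in its narrow form and is minor. As worded, item 10 does not reach Grade 5, and no other item or section makes a related death a DLT except through pneumonitis or an earlier qualifying grade or laboratory value. It is a drafting gap in a stated rule. No sample size, power or alpha figure depends on it.

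The size of any effect on the Phase 2 trigger rests wholly on assumed rates and looks, and on keeping the subject in the denominator. At a low fatal rate it is small: 0.03 percentage points at one look at 21 subjects (0.09 − 0.06) and 1.0 point with a look after every subject (10.6 − 9.6). The large differences in the last row of the table should not be read as expected values. What is left in practice is correct DLT classification in the listing and study report and, for subjects still dosed under Section 8.1, clear wording of the laboratory delay rule. For that rule, the Amendment 3 notes also defer treatment decisions to site standard of care.

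**What to change.** Write item 10 as Grade 4 or 5 (or Grade 4 and above) in 6.1.2.1 and in the synopsis. If the protocol will not be amended again, put one sentence in the SAP or study report stating that related Grade 5 events in the DLT window are DLTs, and set the DLT flag in Listing 16.2.7.1 to match.

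Companion: in 8.1.2.2, write the laboratory delay criterion as Grade 3 and above, keeping the present exceptions and the discontinuation rule in 8.1.4.

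The cost is a few words in two places (or one sentence) and one symbol. The downside is a slightly higher DLT count and a few more dose delays.
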